9.3.1 Source data

See Source data verification plan which will be finalized before start of the study.

9.4 Study agreements

The Principal Investigator at each/the centre should comply with all the terms, conditions, and obligations of the Clinical Study Agreement, or equivalent, for this study. In the event of any inconsistency between this Clinical Study Protocol and the Clinical Study Agreement, the terms of Clinical Study Protocol shall prevail with respect to the conduct of the study and the treatment of patients and in all other respects, not relating to study conduct or treatment of patients, the terms of the Clinical Study Agreement shall prevail.

Agreements between AstraZeneca and the Principal Investigator should be in place before any study-related procedures can take place, or patients are enrolled.

9.4.1 Archiving of study documents

The Investigator follows the principles outlined in the Clinical Study Agreement.

9.5 Study timetable and end of study

The study is expected to start in and to be completed by

At Clean file, data from Visit 1 to Visit 16 will be evaluated and reported in the clinical study report (CSR) including Proof of mechanism biomarkers, CXCL-10 (IP-10) in blood and nasal lavage, and myeloperoxidas, a2-macroglobulin, tryptas, and eosinophilic cationic protein in nasal lavage.

Clinical Study Protocol Drug Substance AZD8848 Study Code D0540C00014 Edition Number 1

End of study is defined as final data base lock which will be performed after the last telephone contact has been completed (Visit 19).

Data from Visit 17 until Visit 19 (lon-term safety follow-up) including ANA, RF, and dsDNA results will be reported separately as an addendum to the CSR. If analysed, data from other exploratory biomarkers will be reported separately from the CSR in an exploratory biomarker summary report.

Any results from genetic research will be reported separately from the CSR.

The study may be terminated at individual centres if the study procedures are not being performed according to GCP, or if recruitment is slow. AstraZeneca may also terminate the entire study prematurely if concerns for safety arise within this study or in any other study with AZD8848.

The study may be halted temporarily, as judged by the clinical centres and AstraZeneca R&D, for instance, parts of the study may be postponed to avoid study conduct when patients risk to be exposed to airborne birch and/or timothy grass pollen.

10. DATA MANAGEMENT BY ASTRAZENECA OR DELEGATE

Data management will be performed by AstraZeneca Data Management Centre Cognizant.

Data will be entered in the WBDC system at the study site. Trained study personnel will be responsible for entering data on the observations, tests and assessments specified in the protocol into the WBDC system and according to the eCRF Instructions. Diary data will be collected by the site and entered electronically in the WBDC system; this would be handled in the same way as the other eCRF data. The eCRF instructions will also guide the study site in performing data entry. Data entered in the WBDC system will be immediately saved to a central database and changes tracked to provide an audit trail. Site personnel will enter the data in the eCRFs. The data will then be Source Data Verified (SDV), reviewed/ queried and updated as needed. The data will be validated as defined in the Data Management Plan.

Quality control procedures will be applied to each stage of data handling to ensure that all data are reliable and have been processed correctly. The principal investigator will then sign the eCRF electronically.

Planned interim clean file occurs when all required modules are received, data have been declared clean, unexpected modules been inactivated till the planned time, data been SDV, reviewed/ queried and updated as needed, all log lines been frozen (except the ongoing loglines) and data signed by the Investigator. The Investigator will sign the eCRF electronically. An interim data copy would be taken in the result database (CAVE) to show the data submitted at the interim clean file. Any treatment revealing data may thereafter be added.

THIS

Clinical Study Protocol Drug Substance AZD8848 Study Code D0540C00014 Edition Number 1

At final clean file all data would be declared clean and signed by the Investigator. Any change in data declared clean during the interim clean file would require an approval and has to be documented. The final database will be locked after the same.

A copy of the eCRF will be archived at the study site when the study has been locked.

Adverse events and medical/surgical history will be classified according to the terminology of the latest version of the Medical Dictionary for Regulatory Activities (MedDRA). Medications will be classified according to the AstraZeneca Drug Dictionary.

Medical coding is done using the most current version of MedDRA and AstraZeneca Drug Dictionary.

Data Management determines the format of the data to be received from external vendors and coordinates the flow of data to an external environment or clinical database (if applicable). Data Management will ensure that the data collection tool will be tested / validated as needed. External data reconciliation will be done with the clinical database as applicable. The data reconciliation will be performed as defined in the Data Management Plan. The data will be validated as defined in the Data Management Plan. Data queries will be raised for inconsistent, impossible or missing data. All entries to the study database will be available in an audit trail.

When all data have been coded, validated, electronically signed by an investigator and locked, clean file will be declared. Any treatment revealing data may thereafter be added and the final database will be locked.

SAE Reconciliation Reports are produced and reconciled with the Patient Safety database and/or the investigational centre.

Genotype data generated in this study will be stored in the AstraZeneca genotyping LIMS database, or other appropriate secure system, within AstraZeneca and/or third party contracted to work with AstraZeneca to analyze samples.

Some or all of the clinical datasets from the main study may be merged with the genetic data in a suitable secure environment separate from the clinical database. The results from this genetic research will be reported separately from the clinical study report for the main study.

11. EVALUATION AND CALCULATION OF VARIABLES BY ASTRAZENECA OR DELEGATE

11.1 Calculation or derivation of efficacy variable(s)

TNSS (recall period 10 min) individual symptoms (runny nose, blocked nose, nasal itching, and sneezing) and PNIF are measured at the clinic at Visit 15 (challenge period) on Days 1 to 7. In addition, TNSS individual symptoms (recall period 12 h) and PNIF are collected by the

THIS

Clinical Study Protocol Drug Substance AZD8848 Study Code D0540C00014 Edition Number 1

patient in the diary from the evening on Day 1 to the morning on Day 8. The challenge period means and means over Days 4 to 7 for TNSS, individual symptoms and PNIF will be calculated by AstraZeneca and the change over time will be evaluated.

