2. STUDY OBJECTIVES

2.1 Primary objective

Table 1 Primary Objective

To compare the efficacy of $60~\mu g$ AZD8848 once weekly with $20~\mu g$ AZD8848 three (3) times weekly and with placebo when administered intranasally to seasonal allergic rhinitis patients out of season in a nasal allergen challenge model.

Variables	Description
Reflective Total Nasal Symptom Score (TNSS) (recall period 12 h, twice daily during Visit 15)	Nasal symptoms
Reflective TNSS (recall period 10 min) after allergen challenge	Nasal symptoms
Peak Nasal Inspiratory Flow (PNIF) (twice daily during Visit 15)	
PNIF 10 min after allergen challenge	

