3.2 Rationale for study design, doses and control groups

Allergic rhinitis patients are included to generate data in one of the potential target populations. A double-blind design is selected to avoid bias resulting from knowledge of the treatment by either patients or centre staff. A randomised placebo control arm is included to obtain reference data to aid interpretation of efficacy, safety, and tolerability. A parallel group design has been chosen to avoid the influence of a potential drug-induced prolonged response (carry-over effect).

The allergen challenge model and the primary endpoints have been chosen to determine if AZD8848 controls nasal inflammation and decreases nasal symptoms. Analysis of local and systemic biomarkers may generate data on mechanisms of action of AZD8848.

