12.3 Determination of sample size

The sample size for this study was selected to be consistent with the research hypothesis as described in Section 1.2.

From previous studies with Rhinocort® in allergic rhinitis using the same provocation model, it has been estimated that the standard deviation for TNSS (both morning and evening) is about 1.5 units. In the preceding Tol/PoP study (D0540C00003), the residual sample standard deviation in the analysis of variance (ANOVA) models was slightly higher however; about 2 units. Since the data from this study will be pooled with the data from the present one we assume a standard deviation of 2 units here too.

A planned total of 70 completed patients in proportions 1:3:1 for the treatments arms $60 \mu g$ AZD8848 once weekly, $20 \mu g$ AZD8848 three times weekly and placebo, respectively, yields 14, 42 and 14 patients respectively in these arms.

Using a one-sided test at 5 % significant level with a sample size of 42 patients in the 20 μ g AZD8848 three times weekly arm and 34+14 = 48 patients in the 60 μ g AZD8848 once weekly arm (obtained after pooling with the Tol/PoP study), with another 34+14 = 48 placebo patients contributing to the estimate of the standard deviation, will then give a 76 % chance to detect a difference of 1 unit between the two AZD8848 arms.

The number of patients that will agree to participate in the genetic research is unknown. It is therefore not possible to establish whether sufficient data will be collected to allow a formal statistical evaluation or whether only descriptive statistics will be generated.

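### Four unranked primary variables with two averaging windows each give eight candidate primary results for the regimen comparison, and a false-positive chance of about 15–28 % where the power calculation assumes 5 %

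*Protocol*

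**What the plan says.** Protocol section 2.1 (Table 1) gives four variables for the primary objective, in no stated order:

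- "Reflective Total Nasal Symptom Score (TNSS) (recall period 12 h, twice daily during Visit 15"
- "Reflective TNSS (recall period 10 min) after allergen challenge"
- "Peak Nasal Inspiratory Flow (PNIF) (twice daily during Visit 15"
- "PNIF 10 min after allergen challenge"

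Section 3.2 confirms that the plural is meant: "The allergen challenge model and the primary endpoints have been chosen to determine if AZD8848 controls nasal inflammation".

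Section 11.1 gives each variable two averages: "The challenge period means and means over Days 4 to 7 for TNSS, individual symptoms and PNIF will be calculated". Neither average has priority.

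Section 12.2 plans ANOVA models for all efficacy variables, with estimates, confidence intervals and p-values. It sets no significance level. The only pairwise differences it lists for estimation are each AZD8848 regimen against placebo.

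Section 12.3 sizes the trial on a different contrast, one AZD8848 regimen against the other, with a one-sided 5 % test, a difference of 1 unit and a standard deviation of 2 units. The variable is TNSS. The starting figure is described thus: "it has been estimated that the standard deviation for TNSS (both morning and evening) is about 1.5 units". No averaging window is given.

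**The concern.** The primary objective compares the two regimens with each other and with placebo, but the protocol does not say which variable and which window carry that comparison. The power statement describes one test, while the text supplies eight results for the same contrast that could each be presented as primary. Reading each at the level used for sizing makes the error rate for the regimen comparison higher than the level behind the 76 %.

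The four variables also answer different questions. The 10-minute measures describe the immediate response to the challenge, and section 1.3 says the Tol/PoP study already showed improvement at that time. The diary measures cover the following 12 and 24 hours. The efficacy limb of the research hypothesis in section 1.2 is a longer-lasting reduction of symptoms. With no ranking, a result on a 10-minute measure alone could be reported as meeting the primary objective while saying little about duration.

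**Working it through.** **Inputs from the protocol.** Section 12.3: 42 patients on 20 µg three times weekly; 34 + 14 = 48 on 60 µg once weekly; 48 on placebo, contributing to the standard deviation; SD 2 units; difference 1 unit; one-sided 5 %; stated power 76 %. Table 1: four variables. Section 11.1: two windows.

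**Inputs assumed, because the documents give none.** Correlation between the test statistics of different variables: 0 to 0.7. Correlation between the two windows of one variable: 0.75 to 0.95.

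**Step 1: reproduce the stated power.** SE = 2 × √(1/42 + 1/48) = 0.4226. Standardised difference = 1 / 0.4226 = 2.366. Normal approximation: Φ(2.366 − 1.645) = Φ(0.721) = 0.765. Noncentral t with 42 + 48 + 48 − 3 = 135 df: 0.761. A two-sided 5 % test would give 0.65 to 0.66. The stated 76 % is therefore the power of a single one-sided 5 % test.

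**Step 2: count the candidate results.** 4 variables × 2 windows = 8 for the regimen contrast. Individual symptom scores are left out because Table 1 does not list them.

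**Step 3: independence as the upper reference.** 1 − 0.95⁸ = 0.337.

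**Step 4: how far the windows overlap.** Days 4–7 lie inside the seven-day period. If a patient's days were independent, the correlation between the 4-day and the 7-day mean would be √(4/7) = 0.756. With within-patient correlation r between days it is √{[r + (1 − r)/7] / [r + (1 − r)/4]}, which is 0.92 at r = 0.3 and 0.96 at r = 0.5. A value near 0.75 is thus about the lowest plausible. Values above 0.95 would lower the results below a little further.

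**Step 5: simulation.** 300,000 draws of eight correlated normal statistics, one-sided threshold 1.645. Chance that at least one exceeds it when the regimens do not differ:

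| Correlation between variables | Windows 0.75 | Windows 0.85 | Windows 0.95 |
|---|---|---|---|
| 0 | 27.7 % | 25.8 % | 22.9 % |
| 0.3 | 24.2 % | 22.6 % | 20.1 % |
| 0.5 | 21.4 % | 19.8 % | 17.6 % |
| 0.7 | 17.8 % | 16.5 % | 14.8 % |

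Two-sided tests at 5 % give 16–29 % over the same grid, so the conclusion does not depend on sidedness.

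**Step 6: what adjustment would cost instead.** Bonferroni over eight tests uses 0.05/8 = 0.00625 each, and power falls to 0.437 (t) or 0.448 (normal). Over the four variables in one window it uses 0.05/4 = 0.0125, and power is 0.541 or 0.550.

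**The case against.** The strongest reply is that this is a phase IIa study with no pass/fail rule. The one-sided 5 % level appears only in the sample-size section. Section 12.2 promises estimates, intervals and p-values, not a decision. Multiplicity and hierarchy are often left to the SAP, which was not available here. That stands in part: the error rates above are conditional on reading each result at the level used for sizing, and the absence of a multiplicity rule is not in itself a fault of the protocol. What the reply does not remove is that choosing the primary variable is a protocol decision, and this protocol has made it by naming four. A SAP that named one would be overriding Table 1 and section 3.2, not filling in a detail.

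It can also be said that section 12.3 already points to the intended variable. Only the 12 h diary score is recorded both morning and evening; the 10-minute score is taken once daily. This is correct, so it would be wrong to say that power is stated for TNSS without distinction. But the hint sits in the sample-size section, leaves the window open, and is not carried into sections 2.1, 11.1 or 12.2.

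A reader might infer three stronger things that the documents do not support:

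- **That a false positive is likely.** For the regimen contrast it stays below one in two even under independence; about 14 independent tests would be needed to pass 50 %.
- **That the tests against placebo should be added to the count.** That is a different null, in which AZD8848 also equals placebo. Sections 1.1 and 1.3 report that it improved symptoms after challenge.
- **That the Day 8 morning score is lost from the late window.** Section 11.1 does not say whether diary records are assigned by calendar day or by challenge, and section 3.1.1 times them from each challenge. On that reading the Day 8 morning score belongs to the seventh challenge and falls inside the window. It is in the whole-period mean in any case.

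**Conclusion.** The point holds in this form. The protocol calls four variables primary, gives each two windows and ranks none, while its power refers to one test. If all eight results for the regimen contrast are read at one-sided 5 %, the chance of at least one false positive is about 15–28 %, roughly three to six times the nominal level. It is at most 34 %, the value under independence, provided the statistics are not negatively correlated.

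The range rests on assumed correlations. It also treats each result as a possible primary finding, which the text permits but does not order. That the power stays at 76 % for a single named analysis further assumes that the 2-unit SD applies to the summary chosen; section 12.3 does not say which TNSS average that SD describes.

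**What to change.** In sections 2.1, 11.1 and 12.2, name one primary analysis that matches the basis of section 12.3: mean 12 h reflective TNSS over all diary records from the evening of Day 1 to the morning of Day 8, 20 µg three times weekly against 60 µg once weekly. Section 12.2 should list that contrast among the differences to be estimated. Label every other variable, window and contrast as supportive, without error control.

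As a minor clarification, state in section 11.1 that diary records are assigned to the Days 4–7 window by challenge.

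The cost is protocol wording only: no change to data collection, visits or sample size. The single test keeps the 5 % error and the 76 % power. The price is that a positive result on another variable or window can no longer be reported as the primary finding.

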11.2 Calculation or derivation of safety variable(s)

See Section 12.2.

11.2.1 Other significant adverse events (OAE)

During the evaluation of the AE data, an AstraZeneca medically qualified expert will review the list of AEs that were not reported as SAEs and DAEs. Based on the expert's judgment, significant adverse events of particular clinical importance may, after consultation with the Global Safety Physician, be considered Other Significant Adverse Events (OAEs) and reported as such in the CSR. Examples of these are marked haematological and other laboratory abnormalities, and certain events that lead to intervention (other than those already classified as serious), dose reduction or significant additional treatment.

11.3 Calculation or derivation of patient reported outcome variables

See Section 11.1.

11.4 Calculation or derivation of pharmacokinetic variables (not applicable)

11.5 Calculation or derivation of pharmacodynamic variable(s)

Biomarkers in nasal lavage and blood are measured at Visit 2 (pre-dose), and at Visit 15 (challenge period) on Day 1 (prior to allergen challenge) and Day 8 (post challenge). The change in biomarkers will be evaluated in three ways:

- during the challenge period calculated as the ratio between the Visit 15 Day 8 and the Visit 15 Day 1 measurements;
- during the treatment period calculated as the ratio between the Visit 15 Day 1 and Visit 2 measurements;
- from before treatment to after the challenge period calculated as the ratio between the Visit 15 Day 8 and the Visit 2 measurements

11.6 Calculation or derivation of pharmacogenetic variables

The number of patients who will agree to participate in the pharmacogenetic research is unknown. It is therefore not possible to establish whether a statistically relevant number of patients will consent to provide sufficient data to be collected to allow a formal statistical evaluation or whether only descriptive statistics will be generated.

Clinical Study Protocol Drug Substance AZD8848 Study Code D0540C00014 Edition Number 1

11.7 Calculation or derivation of health economic variables (not applicable)

12. STATISTICAL METHODS AND SAMPLE SIZE DETERMINATION BY ASTRAZENECA OR DELEGATE

12.1 **Description of analysis sets**

12.1.1 Efficacy analysis set

For evaluation of efficacy and biomarker data, the analysis set will consist of all patients with evaluable efficacy and/or biomarker data from the challenge period (Visit 15).

12.1.2 Safety analysis set

For reporting of safety the full analysis set, as defined in the ICH E9 guideline, will be used, meaning that all randomised and treated (intake of at least 1 dose of investigational product) patients with data after randomisation will be included in the analyses. Thus, patients who were enrolled in the study but never took any dose of investigational product, will not be included in the safety reporting.

12.2 Methods of statistical analyses

All AEs will be listed for each patient and summarized by system organ class and preferred term by using MedDRA vocabulary. AEs will be analysed in terms of descriptive statistics and qualitative analysis.

Safety data will individually be listed and graphically illustrated, presented as descriptive statistics (for example median, mean, range and standard deviation) and mean value plots for each treatment and assessment time. In addition changes in safety variables over time will be presented by shift and scatter plots if existing. Values below and above AstraZeneca extended reference limits will be highlighted.

Efficacy data from this study will be pooled with the same type of data from the Tol/PoP study (D0540C00003), which was virtually identical to the present study in terms of selection criteria and study conduct. The one main difference is that in the present study, women are allowed to participate. The Tol/Pop study featured treatment arms with placebo (n 34) and 60 μg AZD8848 once weekly (n 34) respectively; efficacy data from these arms will be pooled with data from the corresponding arms in the present study.

For all comparisons between treatments the efficacy data (reflective TNSS, individual symptom scores, PNIF) and pharmacodynamic variables (biomarkers in nasal lavage and plasma) will be analysed using analysis of variance (ANOVA) models with treatment and centre as factors and, for biomarkers and clinic PNIF measurements, the baseline value as covariate. When appropriate, multiplicative models will be used.

THIS

Clinical Study Protocol Drug Substance AZD8848 Study Code D0540C00014 Edition Number 1

The covariate in the respective model, the baseline value, will be the last value before first dose of the study drug. From the respective model the pairwise treatment differences between AZD8848 (once weekly and three times weekly, respectively) and placebo will be estimated and confidence intervals and p-values will be calculated. For biomarkers not reported in the CSR, appropriate statistical methods will be used.

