6.2.7 Allergen titration

An allergen titration procedure will be performed at Visit 1 to estimate an individually symptom-producing, tolerable, and repeatable dose for the seven daily nasal allergen challenges to be performed during Visit 15.

The allergen titration will be performed according to standardised procedures and increasing allergen doses will be administered in 10-minute intervals using a nasal spray device. The device delivers $100~\mu L$ per actuation, and one actuation will be sprayed into each nostril, resulting in effective doses of 100, 300, 1000, and 3000 standardized quantity units per nasal cavity. The scheme will be followed until the patient responds with at least 5 sneezes and/or a symptom score of 2 or more, on a scale from 0 to 3 in any of the 2 symptoms of nasal blockage or runny nose. The allergen dose that produced this response will be given to that patient at each daily allergen challenge during Visit 15. The allergen dose will only be recorded as source data in the Investigator study file.

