6.3.2 Reflective Total Nasal Symptom Score (TNSS)

Reflective TNSS represents symptoms over a time period and will be used during allergen challenge (Visit 15) for evaluation of study drug effect.

Clinical Study Protocol Drug Substance AZD8848 Study Code D0540C00014 Edition Number 1

- Reflective TNSS (recall period 10 min): represents symptoms over the last 10 minutes, collected during clinic visits
- Reflective TNSS (recall period 12 h): represents symptoms over the last 12 hours, collected in patient diary

During Visit 15, the patient will record reflective TNSS (recall period 10 min) in a source data sheet. The patients will also record reflective TNSS (recall period 12 h) in a diary every morning and evening from the evening of the first day of challenge, Day 1, until the morning of Day 8. Recording of AEs based on nasal symptoms is described in Section 6.4.3.

For time points of reflective TNSS measurements, see Table 7.

Definition of TNSS

Each individual symptom is scored 0 to 3 and the scores of each symptom (runny nose, blocked nose and the maximum score of nasal itching or sneezing) will be added together to give a TNSS of 0 to 9. The patient will rate the severity of the symptoms runny nose, blocked nose, sneezing, itchy nose and score in a paper source data sheet them according to the following scale:

- 0 = Absence of symptoms: no signs or symptoms evident
- 1 = Mild symptoms: signs or symptoms clearly present, but minimal awareness, easily tolerated
- 2 = Moderate symptoms: definite awareness of signs or symptoms that are bothersome but tolerable
- 3 = Severe symptoms: signs or symptoms that are hard to tolerate, cause interference with activities of daily living and/or sleeping

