6.4.10 Instantaneous TNSS

Instantaneous TNSS represents symptoms at the moment of recording and will be collected as a safety assessment pre-dose and 15 minutes post-dose during Visits 2, 5, 8 and 11.

The patients will be asked to rate the severity of their nasal symptoms (instantaneous TNSS) and record them into a source data sheet. Recording of AEs based on nasal symptoms is described in Section 6.4.3.

For definition of TNSS see Section 6.3.2.

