6.4.11 PNIF

PNIF will be collected as a safety assessment pre-dose and 15 minutes post-dose during Visits 2, 5, 8 and 11. For more information regarding PNIF see Section 6.3.3.

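### Diary PNIF, a variable of the primary objective, is analysed without the Visit 2 pre-dose PNIF that is already collected and already used for clinic PNIF

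*Protocol*

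**What the plan says.** Section 12.2 states that the efficacy and pharmacodynamic variables are "analysed using analysis of variance (ANOVA) models with treatment and centre as factors", with a baseline term added only "for biomarkers and clinic PNIF measurements, the baseline value as covariate". Baseline is defined in the same section: "the baseline value, will be the last value before first dose of the study drug". Section 6.4.11 supplies that value: "PNIF will be collected as a safety assessment pre-dose and 15 minutes post-dose during Visits 2, 5, 8 and 11". Table 6 shows the same schedule.

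Section 2.1 (Table 1) lists two PNIF variables under the primary objective: the clinic reading 10 minutes after each challenge, and the twice-daily reading during Visit 15. Section 6.3.3 puts the twice-daily readings in the patient diary, from the evening of challenge Day 1 to the morning of Day 8. Under Section 12.2 the first of these is baseline-adjusted and the second is not.

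**The concern.** The two PNIF variables measure the same quantity in the same patients in the same week. Peak nasal flow can be expected to differ between people for reasons unrelated to treatment. A pre-treatment reading of that flow is the obvious way to take the difference out of the error term. The plan does this for the clinic readings and, by the wording of its own rule, not for the diary readings. The between-patient spread that the Visit 2 value could explain stays in the residual variance of the diary analysis, and its confidence intervals are wider than they need be.

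The restriction is stated in the protocol and is not a detail left for a later document. It can therefore be judged as it stands.

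**Working it through.** **The plan's own figure.** Section 12.3 sizes the study on TNSS, not PNIF. It takes SD 2, a difference of 1 unit, 42 patients on 20 µg, 34 + 14 = 48 on 60 µg and 48 on placebo, one-sided 5 %, and states 76 % power. The standard error is 2 × sqrt(1/42 + 1/48) = 0.423. Power is 76.5 % by the normal approximation and 76.1 % by the noncentral t with 42 + 48 + 48 - 3 = 135 residual degrees of freedom. The figure reproduces. It says nothing about PNIF, for which the protocol gives no SD and no target difference.

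**Is the covariate available?**
- Present study: yes, planned pre-dose at Visit 2 for every patient (Section 6.4.11, Table 6).
- Earlier study (D0540C00003): the protocol does not say directly. Section 12.2 pools its efficacy data and adjusts clinic PNIF for baseline, so the plan already presupposes that a baseline PNIF exists there.

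**Precision.** Let r be the within-arm correlation between Visit 2 PNIF and the diary PNIF mean. Adjusting multiplies the residual SD, and so the standard error, by sqrt(1 - r²). The same precision without the covariate would need 1/(1 - r²) times the patients.

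| r (assumed) | SE factor | Equivalent sample-size factor |
|---|---|---|
| 0.3 | 0.95 | 1.10 |
| 0.5 | 0.87 | 1.33 |
| 0.7 | 0.71 | 1.96 |

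For example, at r = 0.5, sqrt(1 - 0.25) = 0.866 and 1/0.75 = 1.33. If r were zero, the cost would be one of 135 residual degrees of freedom.

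**Secondary effect: sex mix.** By the wording of Section 12.2, the earlier study did not admit women. It supplies 34 of 48 patients in each pooled arm and none on 20 µg. If a share f of present-study patients are women, the expected share is f on 20 µg and f × 14/48 in each pooled arm. The gap is f × 34/48 = 0.708f. With f = 0.5 (assumed) this is 50 % against 14.6 %, a gap of 0.354.

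If women's PNIF is lower by D (assumed), the unadjusted contrast of 20 µg with either pooled arm is off by 0.354 × D. For D = 30 L/min that is 10.6 L/min. A simulation with f = 0.5, D = 30 and SD 30 L/min gave an unadjusted bias of 10.4 to 10.8 L/min. With baseline PNIF in the model it fell to 4.6, 2.6 and 1.9 L/min at r = 0.5, 0.7 and 0.8. The covariate reduces the bias but does not remove it. The 60 µg and placebo arms have the same make-up (14/48 each from the present study), so their comparison is not affected in expectation.

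**The case against.** The best defence is that the rule adjusts a variable only where a baseline was taken in the same setting. The diary starts on the evening of challenge Day 1, so no diary baseline exists. An ANOVA without the covariate is also valid: among concurrently randomised patients its omission adds no bias. Both facts are right. The second limits the point to precision. The first does not defeat it, because a covariate need only correlate with the outcome, and a clinic reading of the same flow in the same person is a natural candidate.

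A second objection is that every size above rests on assumed values. That stands. The protocol gives no r, no PNIF standard deviation, no sex difference and no expected share of women.

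A reader might go further and infer three things that the protocol does not support:

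- **That TNSS also loses precision for want of a baseline.** Section 6.3.2 confines the efficacy score to the challenge: "Reflective TNSS represents symptoms over a time period and will be used during allergen challenge (Visit 15) for evaluation of study drug effect". The only pre-dose score is the instantaneous one, kept as a safety measure in out-of-season patients (Section 6.4.10). No comparable pre-treatment value exists, and a gain is not shown. Even if r reached 0.2, the 76.1 % power would rise only to 77.6 %.
- **That the titrated allergen dose, or the response to it, is a lost covariate.** Section 6.2.7 does say "The allergen dose will only be recorded as source data in the Investigator study file". But titration brings each patient to a common response threshold, the value of dose as a predictor is not shown, and the protocol does not say whether the data exist for the 34 + 34 = 68 pooled patients.
- **That the missing baseline causes the sex imbalance.** Pooling causes it. Whether it goes uncorrected also depends on how the earlier study's centres enter the centre factor, which the protocol does not state.

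**Conclusion.** The point holds for diary PNIF alone. Section 12.2 withholds from one variable of the primary objective a baseline that is planned for every patient and that the same sentence gives to its clinic counterpart. The consequence is avoidable imprecision, not an invalid test. The standard error with the covariate would be 0.87 times its unadjusted value at r = 0.5 and 0.71 times at r = 0.7. That a repeated flow measurement in one person correlates usefully with itself is a reasonable expectation, but the size of r is an assumption.

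The partial reduction of sex-related bias in the 20 µg contrasts is a side benefit, also of assumed size. It should not be taken as the solution to the pooling problem.

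**What to change.** Reword the covariate clause in Section 12.2 so that Visit 2 pre-dose PNIF is the covariate for both clinic and diary PNIF, with biomarkers unchanged. Confirm that the pooled D0540C00003 data hold the corresponding baseline, which the clinic PNIF model needs in any case.

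The cost is one phrase. No visit, measurement or form is added. Handling of sex or study in the pooled model should be settled separately. A term that separates the two studies would raise the standard error for 20 µg against 60 µg on TNSS from 0.423 to 0.529 and lower the stated 76 % power to 59 %.
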